7.3.1. Cantharidin

Cantharidin is not expected to pose significant occupational safety risk to site staff under proposed conditions of use and administration. Adequate precautions will be taken to avoid direct eye or skin contact and the generation of aerosols or mists. Precaution will be taken to avoid direct contact with the challenge agent. A Material Safety Data Sheet (MSDS) describing occupational hazards and recommended handling precautions will be provided to the investigator. In the case of unintentional occupational exposure, the monitor, medical monitor and/or study manager will be notified.

One part of Cantharone will be mixed with 2.5 parts of pharmaceutical grade acetone in the CUC pharmacy according to standard practice. This reconstituted challenge agent will be used within 4 hours and any residual material will be discarded according to standard GSK waste-streams.

7.3.2. LPS

LPS is not expected to pose significant occupational safety risk to site staff under the proposed conditions of use and administration. Adequate precautions will be taken to avoid direct eye or skin contact and the generation of aerosols or mists. Precaution will be taken to avoid direct contact with the challenge agent. A Material Safety Data Sheet (MSDS) describing occupational hazards and recommended handling precautions will be provided to the investigator. In the case of unintentional occupational exposure, the monitor, medical monitor and/or study manager will be notified.

The dose of LPS will be calculated according to body weight and infused as a bolus over less than 2 minutes. Any residual material will be discarded according to standard GSK waste-streams.

7.3.3. GM-CSF

GM-CSF is not expected to pose significant occupational safety risk to site staff under the proposed conditions of use and administration. Adequate precautions will be taken to avoid direct eye or skin contact and the generation of aerosols or mists. Precaution will be taken to avoid direct contact with the challenge agent. A Material Safety Data Sheet (MSDS) describing occupational hazards and recommended handling precautions will be provided to the investigator. In the case of unintentional occupational exposure the monitor, medical monitor and/or study manager will be notified.

The dose of GM-CSF will be calculated based on body surface area (Mosteller formula: BSA = $0.016667 \times \text{Weight } (\text{kg})^{0.5} \times \text{Height } (\text{cm})^{0.5}$) [Mosteller, 1987] and infused over approximately a 2 hour period. Any residual material will be discarded according to standard GSK waste-streams.

7.4. Treatment Compliance

- When the individual dose for a participant is prepared from a bulk supply, the preparation of the dose will be confirmed by a second member of the study site staff.
- Participants will be dosed at the site and will receive study treatment directly from the investigator or designee, under medical supervision. The date and time of each dose administered in the clinic will be recorded in the source documents and eCRF. The dose of study treatment and study participant identification will be confirmed at the time of dosing by a member of the study site staff other than the person administering the study treatment.

7.5. Concomitant Therapy

Any medication or vaccine (including over-the-counter or prescription medicines, vitamins, and/or herbal supplements) that the participant is receiving at the time of enrolment or receives during the study must be recorded along with:

- reason for use
- dates of administration including start and end dates
- dosage information including dose and frequency

The Medical Monitor should be contacted if there are any questions regarding concomitant or prior therapy.

Participants must abstain from taking prescription or non-prescription drugs (including paracetamol, NSAIDs, steroids, vitamins and dietary or herbal supplements) within 7 days (or 14 days if the drug is a potential enzyme inducer) or 5 half-lives (whichever is longer) before the start of study treatment until completion of the follow-up visit, unless, in the opinion of the investigator and sponsor, the medication will not interfere with the study.

Other concomitant medication may be considered on a case-by-case basis by the investigator in consultation with the Medical Monitor if required.

8. DISCONTINUATION CRITERIA

8.1. Withdrawal from the Study

- A participant may withdraw from the study at any time at his/her own request, or may be withdrawn at any time at the discretion of the investigator for safety, behavioural, compliance or administrative reasons.
- If the participant withdraws consent for disclosure of future information, the sponsor may retain and continue to use any data collected before such a withdrawal of consent.
- If a participant withdraws from the study, he/she may request destruction of any samples taken and not tested, and the investigator must document this in the site study records.

- Refer to the SoA for data to be collected at the time of study discontinuation and follow-up and for any further evaluations that need to be completed.
- Individual participants may be withdrawn from the study if, in the judgement of the investigator, they have exhibited symptoms in response to LPS or GM-CSF that are exaggerated or unanticipated.

8.2. Lost to Follow Up

A participant will be considered lost to follow-up if he or she repeatedly fails to return for scheduled visits and is unable to be contacted by the study site.

The following actions must be taken if a participant fails to return to the clinic for a required study visit:

- The site must attempt to contact the participant and reschedule the missed visit as soon as possible and counsel the participant on the importance of maintaining the assigned visit schedule and ascertain whether or not the participant wishes to and/or should continue in the study.
- Before a participant is deemed lost to follow up, the investigator or designee must make every effort to regain contact with the participant (where possible, 3 telephone calls and, if necessary, a certified letter to the participant's last known mailing address or local equivalent methods). These contact attempts should be documented in the participant's medical record.
- Should the participant continue to be unreachable, he/she will be considered to have withdrawn from the study with a primary reason of lost to follow-up.

9. STUDY ASSESSMENTS AND PROCEDURES

- Study procedures and their timing are summarized in the SoA (Section 2).
- Protocol waivers or exemptions are not allowed
- Immediate safety concerns should be discussed with the sponsor immediately upon occurrence or awareness to determine if the participant should continue or discontinue study treatment.
- Samples will be stored securely and made accessible only to scientists contributing to and supporting this research. Clear custodianship responsibilities will be in place at all times and receipt/use/disposal details will be tracked on databases as per GSK internal processes. The samples will be stored for a maximum of 5 years, after which they will be disposed of in accordance with the Human Tissue Authority's Code of Practice.
- Adherence to the study design requirements, including those specified in the SoA, is essential and required for study conduct.
- All screening evaluations must be completed and reviewed to confirm that potential participants meet all eligibility criteria. The investigator will maintain a screening log to record details of all participants screened and to confirm eligibility or record reasons for screening failure, as applicable.

- The maximum amount of blood collected from each participant over the duration of the study, including any extra assessments that may be required, will not exceed 500 mL.
- Repeat or unscheduled samples may be taken for safety reasons or for technical issues with the samples.

9.1. Adverse Events

The definitions of an AE or SAE can be found in Appendix 4.

The investigator and any designees are responsible for detecting, documenting, and reporting events that meet the definition of an AE or SAE and remain responsible for following up AEs that are serious, considered related to the study treatment or the study, or that caused the participant to discontinue the study.

9.1.1. Time Period and Frequency for Collecting AE and SAE Information

- All SAEs will be collected from the time when the ICF is signed by the participants until the follow-up visit at the time points specified in the SoA (Section 2).
- All AEs will be collected from the start of session 1 until the follow-up visit at the time points specified in the SoA (Section 2).
- Medical occurrences that begin before the start of study treatment but after obtaining informed consent will be recorded on the Medical History/Current Medical Conditions section of the case report form (CRF) not the AE section.
- All SAEs will be recorded and reported to the sponsor or designee immediately and under no circumstance should this exceed 24 hours, as indicated in Appendix 4. The investigator will submit any updated SAE data to the sponsor within 24 hours of it being available.
- Investigators are not obligated to actively seek AEs or SAEs in former study participants. However, if the investigator learns of any SAE, including a death, at any time after a participant has been discharged from the study, and he/she considers the event to be reasonably related to the study treatment or study participation, the investigator must promptly notify the sponsor.
- The method of recording, evaluating, and assessing causality of AEs and SAEs and the procedures for completing and transmitting SAE reports are provided in Appendix 4.

9.1.2. Method of Detecting AEs and SAEs

Care will be taken not to introduce bias when detecting AE and/or SAE. Open-ended and non-leading verbal questioning of the participant is the preferred method to inquire about AE occurrence.

9.1.3. Follow-up of AEs and SAEs

After the initial AE/SAE report, the investigator is required to proactively follow each participant at subsequent visits/contacts. All SAEs will be followed until the event is resolved, stabilized, otherwise explained, or the participant is lost to follow-up (as defined in Section 8.2). Further information on follow-up procedures is given in Appendix 4.

9.1.4. Regulatory Reporting Requirements for SAEs

- Prompt notification by the investigator to the sponsor of a SAE is essential so that legal obligations and ethical responsibilities towards the safety of participants and the safety of a study treatment under clinical investigation are met.
- The sponsor has a legal responsibility to notify both the local regulatory authority and other regulatory agencies about the safety of a study treatment under clinical investigation. The sponsor will comply with country-specific regulatory requirements relating to safety reporting to the regulatory authority, Institutional Review Boards (IRB)/Independent Ethics Committees (IEC), and investigators.
- Investigator safety reports must be prepared for suspected unexpected serious adverse reactions (SUSAR) according to local regulatory requirements and sponsor policy and forwarded to investigators as necessary.
- An investigator who receives an investigator safety report describing a SAE or other specific safety information e.g. summary or listing of SAE) from the sponsor will review and then file it along with the Investigator's Brochure and will notify the IRB/IEC, if appropriate according to local requirements.

9.2. Treatment of Overdose

Cantharidin: Treatment of Challenge Agent Overdose

- Participants will not have access to cantharidin and overdose is therefore extremely unlikely. In the event of overdose, the clinical management will be based on symptomatic treatment and supportive measures as indicated and required according to current UK guidelines.
- In case of any overexposure to Cantharone refer to Material Safety Data Sheet (MSDS).
- Inhalation: Remove victim to fresh air. Give oxygen or artificial respiration if necessary.
- Skin Contact: Immediately flood affected skin with water while removing and isolating all contaminated clothing. Gently wash all affected skin areas thoroughly with soap and water. Seek medical attention if warranted.

CONFIDENTIAL

- Eye Contact: First check the victim for contact lenses and remove if present. Flush victim's eyes with water or normal saline solution for 20 to 30 minutes while simultaneously calling a hospital or poison control centre. Do not put any ointments, oils, or medication in the victim's eyes without specific instructions from a physician. Immediately transport the victim after flushing eyes to a hospital even if no symptoms (such as redness or irritation) develop.
- Ingestion: Do not induce vomiting. If the victim is conscious and not convulsing, give 1 or 2 glasses of water to dilute the chemical and immediately call a hospital or poison control centre. Immediately transport the victim to a hospital. If the victim is convulsing or unconscious, do not give anything by mouth, ensure that the victim's airway is open, and lay the victim on his/her side with the head lower than the body. Transport the victim immediately to a hospital.

LPS: Treatment of Challenge Agent Overdose

- LPS dose selection has been made on the basis of a lower dose and potency than is usually reported in the literature, and thus overdose is not anticipated.
- Intravenous LPS has the potential to be extremely harmful in overdose and induce symptoms and organ dysfunction in keeping with septic shock. Participants who receive an overdose of intravenous LPS will be hydrated with rapid intravenous fluid boluses. Clinical staff may need to expedite immediate transfer to hospital in the event that volunteers exhibit clinical signs of septic shock. Mild pyrexia and malaise may be observed.

GM-CSF: Treatment of Challenge Agent Overdose

• In case of overdose, participant will be carefully monitored for WBC increase and respiratory symptoms. Symptomatic management will be carried out according to existing guidelines.

9.3. Safety Assessments

Planned time points for all safety assessments are provided in the SoA.

9.3.1. Height and body weight

Height and body weight will be measured and recorded in PIMS. Body weight at session 2 Day -1 will be used to calculate the dose of LPS and GM-CSF to be used.

9.3.2. Physical Examinations

- A complete physical examination will include, at a minimum, assessments of the skin, cardiovascular, respiratory, gastrointestinal and neurological systems.
- A brief physical examination will include, at a minimum, assessments of the skin, lungs, cardiovascular system and abdomen (liver and spleen).

9.3.3. Assessment of blister sites

• Visual assessment of blister site will be carried out at selected visits.

9.3.4. Vital Signs

- Vital sign measurements will include systolic and diastolic blood pressure, respiratory rate, SpO2 and pulse rate.
- Blood pressure and pulse measurements will be assessed in a semi-supine position with a completely automated device. Manual techniques will be used only if an automated device is not available.
- Blood pressure and pulse measurements should be preceded by at least 5 minutes of rest for the participant in a quiet setting in a semi supine position without distractions (e.g., television, cell phones).
- Vital signs (to be taken before blood collection for laboratory tests at times detailed in SoA) will consist of 1 pulse and 1 blood pressure measurement.
- Temperature will also be taken

9.3.5. Electrocardiograms

- Triplicate 12-lead ECG will be obtained at screening and baseline as outlined in the SoA using an ECG machine that automatically calculates the heart rate and measures PR, QRS, QT, and QTc intervals. At all other time points a single ECG measurement will be taken.
- All scheduled time points for ECG measurements should be preceded by at least 5 minutes of rest for the participant in a quiet setting in a semi supine position without distractions (e.g., television, cell phones).
- At each time point at which triplicate ECG are required, 3 individual ECG tracings will be obtained as closely as possible in succession.
- Participants dosed with LPS, will receive telemetry for a minimum of 6 hours post-dose or until their telemetry shows no clinical significant findings for 4 hours (whichever is longer).
- Participants undergoing the GM-CSF challenge may be connected to continuous cardiac telemetry during their stay in the unit at the discretion of the investigator if they are symptomatic.

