	most frequent occurring AEs were headache, and feeling cold. No clinically relevant changes or unexpected treatment-related trends were observed in supine systolic and diastolic blood pressure, body temperature, or ECG-derived parameters following administration of LPS. LPS can dose-dependently increase body temperature and heart rate, with a maximal increase amounting approximately 1.5 °C and 28 \pm 13.2 bpm for LPS dose of 2 ng/kg (10 EU/ng) tested, observed at 3–4 hours after LPS administration (Dillingh, 2014).	During the dose finding phase of the study only one participant will be dosed at a time with LPS. The participants will be dosed with LPS in a MHRA accredited clinical research unit and will have regular monitoring of vital signs post dose. The frequency of monitoring can be increased if there are clinical concerns. The dosed participants will be confined to clinical unit for approx. 24 hours post dosing with LPS. The age range for participants in this study is restricted to 18-45 years old to minimise the
		possibility of exaggerated response to LPS. Participants will receive telemetry for a minimum of 6 hours post-dose or until their telemetry shows no clinical significant findings for 4 hours (whichever is longer).
		Participants will be prehydrated with intravenous fluids prior to LPS challenge, and intravenous fluid hydration will continue following the challenge. Normal saline will be infused at a rate of 250ml/hr for 4 hours prior to LPS dosing and 8 hours subsequently.
Risk of severe vagal response	IV LPS endotoxin challenge has been administered in the higher dose range of 2 - 4 ng/kg (10 EU/ng) to thousands of individuals with	Participants with previous history of vasovagal syncope will be excluded from the study.
		Participants will be pre-hydrated with intravenous

Potential Risk of Clinical Significance	Summary of Data/Rationale for Risk	Mitigation Strategy	

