Risk of Respiratory Symptoms	Sequestration of granulocytes in the pulmonary circulation has been documented following LEUKINE infusion12 and dyspnoea has been reported occasionally in patients treated with LEUKINE. Special attention should be given to respiratory symptoms during or immediately following LEUKINE infusion, especially in patients with pre-existing lung disease. In patients displaying dyspnoea during LEUKINE administration, the rate of infusion should be reduced by half. If respiratory symptoms worsen despite infusion rate reduction, the infusion should be discontinued. Subsequent IV infusions may be administered following the standard dose schedule with careful monitoring. LEUKINE should be administered with caution in patients with hypoxia.	Patients with known respiratory disease will be excluded from the study (as described in the Exclusion criteria), as well as patients with current or recent (<30 days) infection.
Risk of cardiovascular Symptoms	Occasional transient supraventricular arrhythmia has been reported in uncontrolled studies during LEUKINE administration, particularly in patients with a previous history of cardiac arrhythmia. However, these arrhythmias have been reversible after discontinuation of LEUKINE.	Patients with pre-existing cardiac disease will not be eligible to participate. In addition, we will use telemetry for a minimum of 6 hours following dosing, or until normal for 4 hours (whichever is longer).

2016N309726_01

CONFIDENTIAL

Potential Risk of Clinical Significance	Summary of Data/Rationale for Risk	Mitigation Strategy
	LEUKINE should be used with caution in patients with pre-existing cardiac disease.	

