3.4.3. Overall Benefit : Risk Conclusion

The measures taken to minimize the potential risks identified in association with cantharidin, LPS and GM-CSF are considered sufficient to justify participation by healthy volunteer participants.

[figure not shown]

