Day:	Within 30 days of Day 1				Minimum 2 wks (max 4 weeks) after end of session 1					Minimum 2 wks (max. 4 weeks) after end of session 2	Approx. 5wks after end of session 2	
stimulation blood sample												following time points: Pre challenge, 40 mins, 2hr:40mins and 5hr:40mins (and 9hr 40mins for GM-CSF for flow cytometry only) with respect to start of blister induction
Transcriptomic blood sample							X 					10. Ex vivo stimulation blood sample: 2 samples (one null and one LPS tube) to be taken pre-dose and 2 samples (one null and one LPS tube) to be taken at 5hrs:40mins post blister induction
Urine sampling for PD			X 				X 					11. Pre-challenge urine sample will be collected in session 1. For the post-challenge samples in session 2, participants will be encouraged to pass urine immediately before LPS dosing and each urine void will be collected after LPS until 12 hours post-LPS
For LPS only: Intravenous hydration with normal Saline at a rate of 250 mL / hr							X 					12. From 4 hours prior to LPS until 8 hours after LPS
In vivo LPS or GM-CSF challenge							X 					
Blister sample for biomarkers			X	X				X	X			
Pain rating 				X					X			
Participant diary card given to participant to record blister healing		X					X					

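### Protocol 9.3.5 makes GM-CSF telemetry discretionary and symptom-triggered, while the risk table in 3.4.1 promises it unconditionally for at least 6 hours

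*Protocol*

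**What the plan says.** Protocol 3.4.1 (Risk Assessment), in the cardiovascular row of its GM-CSF block, names the risk: "Occasional transient supraventricular arrhythmia has been reported in uncontrolled studies during LEUKINE administration". The same row says this was seen mainly in patients who had had arrhythmia before, and that it resolved once the drug was stopped. Two mitigations follow. The first is exclusion of people with cardiac disease. The second is monitoring: "we will use telemetry for a minimum of 6 hours following dosing, or until normal for 4 hours (whichever is longer". No symptom condition or discretion is attached.

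Protocol 9.3.5 (Electrocardiograms) has one telemetry bullet per agent. For LPS it is mandatory: "Participants dosed with LPS, will receive telemetry for a minimum of 6 hours post-dose". For GM-CSF it reads "Participants undergoing the GM-CSF challenge may be connected to continuous cardiac telemetry during their stay in the unit at the discretion of the investigator", and the sentence ends by limiting this to participants with symptoms: "at the discretion of the investigator if they are symptomatic".

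The Schedule of Activities (Protocol section 2, reproduced in SAP 10.1.1) has a telemetry row marked on Session 2 Day 1. It carries no arm label, footnote or duration. Protocol section 9 makes adherence to the Schedule mandatory, and 9.3 refers to it for the timing of safety assessments.

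Protocol 3.4.3 concludes that the measures taken for cantharidin, LPS and GM-CSF "are considered sufficient to justify participation by healthy volunteer participants".

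**The concern.** The section that tells the site what to do withdraws, for one agent, a safeguard that the risk table says will be used. Telemetry started only once symptoms appear cannot detect an arrhythmia that causes none. The participants are healthy volunteers who gain nothing from taking part (3.4.2), so the benefit-risk conclusion in 3.4.3 rests on the listed measures being delivered. As written, two investigators could each follow a section of the protocol and monitor the same asymptomatic participant differently.

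This is a participant-safety and consistency matter. Telemetry feeds no endpoint, sample-size figure or planned analysis.

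**Working it through.** The plan gives no figure to reproduce. The check sets the texts side by side and then counts what each guarantees.

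| Source | Agent | Condition | Duration |
|---|---|---|---|
| 3.4.1, LPS row | LPS | none | at least 6 h, or until 4 h clear, whichever is longer |
| 9.3.5, LPS bullet | LPS | none | same |
| 3.4.1, GM-CSF cardiovascular row | GM-CSF | none | at least 6 h, or until 4 h normal, whichever is longer |
| 9.3.5, GM-CSF bullet | GM-CSF | symptoms and investigator discretion | no minimum |
| Schedule, telemetry row | not named | none | none stated |

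**Where the mismatch lies.** For LPS, 3.4.1 says "Participants will receive telemetry for a minimum of 6 hours post-dose or until their telemetry shows no clinical significant findings for 4 hours" and 9.3.5 repeats the rule almost word for word. The conflict is confined to GM-CSF.

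**Guaranteed telemetry, asymptomatic GM-CSF participant.** Under 3.4.1: 6 h × 60 = 360 minutes at least. Under 9.3.5 read alone: 0 minutes. Under the Schedule: some telemetry on Day 1, with no minimum.

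**Scheduled cover without telemetry, first 6 hours after challenge.** Schedule footnote 8 sets vital signs half-hourly to 4 hours, then hourly to 8 hours.
- First 4 hours: 4 h ÷ 0.5 h = 8 sets.
- Hours 5 and 6: 2 sets.
- Total: 8 + 2 = 10 sets, spaced 30 to 60 minutes apart.

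Under 9.3.4 each set has one pulse and one blood pressure reading, and vital signs also include respiratory rate, SpO2 and temperature. The Day 1 ECG is not counted, because the Schedule gives it no clock time and it could precede dosing.

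**Participants affected.** Protocol 5.1 allows up to 4 GM-CSF participants in Part II. SAP 3.2 opens that part only if at least one participant's maximum leukocyte rise is below 5 giga/L, and all available biomarker data are considered first.

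**When the 6 hours start.** LPS is injected over 1 to 2 minutes, so the starting point hardly matters. GM-CSF is infused over about 2 hours (7.1, 7.3.3), and 3.4.1 does not say whether its 6 hours run from the start or the end.
- From the start: 6 − 2 = 4 h of cover after the infusion ends.
- From the end: the infusion itself is uncovered, although 3.4.1 places the arrhythmia during administration.
- Infusion plus 6 h afterwards: 2 + 6 = 8 h per participant, and 4 × 8 = 32 participant-hours. The bare 6-hour minimum would be 4 × 6 = 24.

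**The case against.** The strongest reply is that the Schedule already settles the matter. Its telemetry row is unrestricted, two other rows are expressly headed as LPS only, and section 9 makes adherence to the Schedule mandatory. A site working from it would use telemetry in both arms. This stands to the extent that zero telemetry arises only if 9.3.5 is followed on its own.

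It does not remove the conflict. The Schedule sets no duration, and no text ranks it above 9.3.5. A missing arm label is also not conclusive: the urine row has none either, yet its footnote 11 ties post-challenge collection to LPS alone ("each urine void will be collected after LPS until 12 hours post-LPS"). The telemetry row lacks such a footnote, so the Schedule supports 3.4.1 without proving it.

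The second reply is that the risk is low, and most of this stands. The arrhythmia is described as occasional, transient and reversible, and as concentrated in people with earlier arrhythmia. Cardiac disease is excluded under 6.2. A single dose of 60 µg/m² is 60 ÷ 250 = 24% of the recommended daily 250 µg/m² given in 5.5.3. Vital signs can be taken more often if symptoms occur, and timed blood draws also bring staff to the participant. None of this restores the continuous monitoring that 3.4.1 promises.

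A reader might infer that Part I GM-CSF participants went without telemetry, or that arrhythmias were missed. The documents support neither inference. They do not show what was done in Part I, and they give no arrhythmia rate for healthy volunteers at 60 µg/m².

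**Conclusion.** The contradiction is real and both halves are current protocol text. Confidence is high that the wording conflicts. It is lower that monitoring would actually be lost, because that depends on whether a site follows 9.3.5 or the Schedule.

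The consequence is limited to whether asymptomatic participants are monitored continuously, in a small conditional group with other safeguards in place. A reader might infer that the benefit-risk conclusion fails. That goes too far: telemetry is one of several measures behind 3.4.3, and in its own row it is listed after the cardiac exclusion. The point still deserves correction before any further GM-CSF dosing, since a promised safeguard for healthy volunteers should not depend on which section is read.

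The participant count assumes that all 4 Part II GM-CSF places are filled. The 8-hour figure assumes a 2-hour infusion and no finding that prolongs monitoring.

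**What to change.** Before any Part II GM-CSF dosing:

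1. Replace the optional GM-CSF bullet in 9.3.5 with a requirement. Every GM-CSF participant is on telemetry from the start of the 2-hour infusion until at least 6 hours after the infusion ends, or until the trace has been clear of clinically significant findings for 4 hours, whichever is longer.
2. Add the same duration as a footnote to the telemetry row of the Schedule of Activities.

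Copying the LPS rule unchanged would not be enough. Its post-dose wording suits a 1 to 2 minute injection, and could leave out the infusion, which is when the risk table places the arrhythmia.

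If discretionary telemetry was intended, the sponsor should instead amend the 3.4.1 commitment and justify dropping it.

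The telemetry time is the 8 hours per participant shown above. It falls within the overnight stay already scheduled for Session 2 Day 1 and uses equipment the unit already runs for LPS. No participants, samples or endpoints are added. Rewording 9.3.5 probably needs a short amendment with IEC/IRB approval (Appendix 3). The Schedule footnote may not, since section 2 lets documented, approved timing changes be made without one.
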